9.2 Adverse Event Monitoring

9.2.1 Definitions (per 21 CFR 312.32(a))

Adverse event: “Any untoward medical occurrence associated with the use of a drug in humans, whether or not considered drug related.”

This includes the following:

1. Aes not previously observed in the subject that emerge during the protocol-specified AE reporting period, including signs or symptoms associated with study treatment that were not present prior to the AE reporting period.
2. Complications that occur as a result of protocol-mandated interventions (e.g., invasive procedures such as tumor biopsy).
3. If applicable, Aes that occur prior to assignment of study treatment associated with medication washout, no treatment run-in, or other protocol-mandated intervention.
4. Preexisting medical conditions (other than the condition being studied) judged by the investigator to have worsened in severity or frequency or changed in character during the protocol-specified AE reporting period.

Life-threatening adverse event or life-threatening suspected adverse reaction: “An adverse event or suspected adverse reaction is considered “life threatening” if, in the view of either the investigator or sponsor, its occurrence places the patient or subject at immediate risk of death. It does not include an adverse event or suspected adverse reaction that, had it occurred in a more severe form, might have caused death.”

Serious adverse event or serious suspected adverse reaction: “An adverse event or suspected adverse reaction is considered “serious” if, in the view of either the investigator or sponsor, it results in any of the following outcomes:

- Death,
- A life-threatening adverse event,
- Inpatient hospitalization or prolongation of existing hospitalization,
- A persistent or significant incapacity or substantial disruption of the ability to conduct normal life functions, or A congenital anomaly/birth defect. Important medical events that may not result in death, be life-threatening, or require hospitalization may be considered serious when, based upon appropriate medical judgment, they may jeopardize the patient or subject and may require medical or surgical intervention to prevent one of the outcomes listed in this definition. Examples of such medical events include allergic bronchospasm requiring intensive treatment in an emergency room or at home, blood dyscrasias or convulsions that do not result in inpatient hospitalization, or the development of drug dependency or drug abuse.”

Suspected adverse reaction: “Suspected adverse reaction means any adverse event for which there is a reasonable possibility that the drug caused the adverse event. For the purposes of IND safety reporting, “Reasonable possibility” means there is evidence to suggest a causal relationship between the drug and the adverse event. Suspected adverse reaction implies a lesser degree of certainty about causality than adverse reaction, which means any adverse event caused by a drug.”

Unexpected adverse event or unexpected suspected adverse reaction: “An adverse event or suspected adverse reaction is considered “unexpected” if it is not listed in the investigator brochure or is not listed at the specificity or severity that has been observed; or, if an investigator brochure is not required or available, is not consistent with the risk information described in the general investigational plan or elsewhere in the current application, as amended. For example, under this definition, hepatic necrosis would be unexpected (by virtue of greater severity) if the investigator brochure referred only to elevated hepatic enzymes or hepatitis. Similarly, cerebral thromboembolism and cerebral vasculitis would be unexpected (by virtue of greater specificity) if the investigator brochure listed only cerebral vascular accidents. “Unexpected,” as used in this definition, also refers to adverse events or suspected adverse reactions that are mentioned in the investigator brochure as occurring with a class of drugs or as anticipated from the pharmacological properties of the drug, but are not specifically mentioned as occurring with the particular drug under investigation.”

The descriptions and grading scales found in the revised NCI Common Terminology Criteria for Adverse Events (CTCAE) version 5.0 will be utilized for AE reporting. All appropriate treatment areas should have access to a copy of the CTCAE version 5.0. A copy of the CTCAE version 5.0 can be downloaded from the CTEP web site (<http://ctep.cancer.gov>).

Events or Outcomes Not Qualifying as Serious Adverse Events

The following are not considered SAEs and therefore do not need to be reported as such:

- Pre-planned or elective hospitalization including social and/ or convenience situations
- Hospital visits of less than 24 hours duration (eg, patient presents to the emergency room, but is not admitted to a ward)
- Overdose of either avelumab, intravesical-BCG or concomitant medication unless the event meets SAE criteria (eg, hospitalization). However, the event should still be captured as a non-serious AE
- Events of progression of the patient’s underlying cancer as well as events clearly related to progression of the patient’s cancer (signs and symptoms of progression) should not be reported as a serious adverse event unless the outcome is fatal within the safety reporting period. If the event has a fatal outcome within the safety reporting period, then the event of Progression of Disease must be recorded as an AE and as a SAE with CTCAE Grade 5 (fatal outcome) indicated.

9.2.2 Definition of an Adverse Events of Special Interest

AESIs (serious or non-serious) are defined as AEs of scientific and medical concern specific to a product or program, for which ongoing monitoring and rapid communication can be appropriate. Such an event might warrant further investigation in order to characterize and understand it. Depending on the nature of the event, rapid communication by the Sponsor-Investigator to other parties (eg, regulators) might also be warranted.

Serious AESIs shall be forwarded to EMD Serono within 2 business days or 3 calendar days (whichever comes first) of the awareness date. Others shall be sent within thirty (30) calendar days.

9.2.2.1 Adverse Events of Special Interest for Avelumab

The adverse events of special interest for avelumab are summarized in tables 2-4 and detailed information can be found in avelumab Investigator’s Brochure.

9.2.3 Clinical Laboratory Assessments as Adverse Events and Serious Adverse Events

An abnormal laboratory value that is not already associated with an AE is to be recorded as an AE only if any one of the following criteria is met:

- an action on the study drug is made as a result of the abnormality
- intervention for management of the abnormality is required
- at the discretion of the investigator should the abnormality be deemed clinically significant

9.2.4 Pregnancy or Breastfeeding

If a patient becomes pregnant or breastfeeding while receiving avelumab or within 5 months after the last dose of avelumab, a report should be completed and expeditiously report to sponsor/principal investigator. Follow-up to obtain the outcome of the pregnancy should also occur.

Abortion, whether accidental, therapeutic, or spontaneous, should always be classified as serious, and expeditiously reported to sponsor/principal investigator, as an SAE. Similarly, any congenital anomaly/birth defect in a child born to a female subject exposed to the avelumab should be reported to sponsor/principal investigator as an SAE.

Pregnancy reports: While such reports are not serious Aes or ADRs per se, as defined herein, any reports of pregnancy, where the fetus may have been exposed to the Product, shall be transmitted to Sponsor/Principal investigator within 2 business days or 3 calendar days of the awareness date (whichever comes first) using the applicable safety report form provided. Meantime, such reports shall be forwarded to EMD Serono within 2 business days or 3 calendar days (whichever comes first) of the awareness date. Pregnancies will be followed up until the outcome of the pregnancy is known, whenever possible, based upon due diligence taken to obtain the follow-up information.

9.3 Documenting Adverse Events

All Aes information must be documented on the appropriate AE case report form. Additional follow-up information (e.g., test results, autopsy, and discharge summary) may be obtained to supplement AE reports. A copy of all initial and follow-up reports will be included with the patient's study files.

9.3.1 Specific Instructions for Recording Adverse Events

Investigators should use correct medical terminology/concepts when reporting Aes or SAEs. Avoid colloquialisms and abbreviations.

Diagnosis versus Signs and Symptoms: If known at the time of reporting, a diagnosis should be reported rather than individual signs and symptoms (e.g., record only liver failure or hepatitis rather than jaundice, asterixis, and elevated transaminases). However, if a constellation of signs and/or symptoms cannot be medically characterized as a single diagnosis or syndrome at the time of reporting, it is acceptable to report the information that is currently available. If a diagnosis is subsequently established, it should be reported as follow-up information.

Deaths: All deaths that occur during the protocol-specified AE reporting period, regardless of attribution, will be reported to the appropriate parties. When recording a death, the event or condition that caused or contributed to the fatal outcome should be reported as the single medical concept. If the cause of death is unknown and cannot be ascertained at the time of reporting, report "Unexplained Death".

Preexisting Medical Conditions: A preexisting medical condition is one that is present at the start of the study. Such conditions should be reported as medical and surgical history. A preexisting medical condition should be re-assessed throughout the trial and reported as an AE or SAE only if the frequency, severity, or character of the condition worsens during the study. When reporting such events, it is important to convey the concept that the preexisting condition has changed by including applicable descriptors (e.g., “more frequent headaches”).

Hospitalizations for Medical or Surgical Procedures: Any AE that results in hospitalization or prolonged hospitalization should be documented and reported as an SAE. If a subject is hospitalized to undergo a medical or surgical procedure as a result of an AE, the event responsible for the procedure, not the procedure itself, should be reported as the SAE. For example, if a subject is hospitalized to undergo coronary bypass surgery, record the heart condition that necessitated the bypass as the SAE.

Hospitalizations for the following reasons do not require reporting:

- Hospitalization or prolonged hospitalization for diagnostic or elective surgical procedures for preexisting conditions
- Hospitalization or prolonged hospitalization required to allow efficacy measurement for the study or
- Hospitalization or prolonged hospitalization for scheduled therapy of the target disease of the study

9.4 Causality Assessment of Adverse Events

The relationship between an AE and the study drug will be determined by the Investigator on the basis of his or her clinical judgment and the following definitions.

An AE will be considered associated with the use of study drug if there is a reasonable possibility that the AE may have been caused by the study drug. This definition applies to those AEs that are considered definitely, probably, and possibly related to the use of the study drug:

Definitely Related: An AE that follows a temporal sequence from administration of the study drug; follows a known response pattern to the study drug; improves after stopping the study drug (positive dechallenge) and reappears after repeat exposure (positive rechallenge); and cannot be reasonably explained by known characteristics of the patient’s clinical state or by other therapies

Probably Related: An AE that follows a reasonable temporal sequence from administration of the study drug; follows a known response pattern to the study drug; improves after dechallenge; and cannot be reasonably explained by the known characteristics of the patient’s clinical state or by other therapies.

Possibly Related: An AE that follows a reasonable temporal sequence from administration of the study drug and follows a known response pattern to the study drug but could have been produced by the patient’s clinical state or by other therapies. An AE may be considered not associated with the use of study drug if there is not a reasonable possibility that the AE may have been caused by the study drug. This definition applies to those AEs that are considered unlikely or not related to the use of the study drug:

Unlikely to be Related: An AE assessed as unlikely to be related to study drug is defined as an AE for which sufficient information exists to indicate a high improbability that the event is related to the study drug.

Not Related: An AE assessed as not related to study drug is defined as an AE for which sufficient information exists to indicate that the etiology is unrelated to the study drug. Two or more of the following variables apply:

- The AE does not follow a reasonable temporal sequence after administration of the study drug.
- The AE is readily explained by the patient's clinical state or other therapies.
- Negative dechallenge—the AE does not abate upon dose reduction or cessation of therapy (assuming that it is reasonable to expect abatement of the AE within the observed interval).

9.5 Severity Assessment of Adverse Events

Severity of AEs will be graded according to the CTCAE Version 5.0.

Adverse events not included in the CTCAE, Version 5.0 must be graded as follows: Mild, Moderate, Severe, Life-threatening, and Fatal according to the following definitions:

- Mild: The AE is noticeable to the patient but does not interfere with routine activity.
- Moderate: The AE interferes with routine activity but responds to symptomatic therapy or rest.
- Severe: The AE significantly limits the patient's ability to perform routine activities despite symptomatic therapy.
- Life-threatening: The AE places the patient at risk of death at the time of the event.
- Fatal: The AE results in the death of the patient.

9.6 Study Monitoring

All aspects of the study will be carefully monitored at periodic intervals throughout the study per FDA "Guidance for Industry – E6 (R2) Good Clinical Practice: Integrated Addendum to ICH E6 (R1)" dated March 2018. All Case Report Forms (CRFs) will be up to 100% source verified against corresponding source documentation (e.g., office and clinical laboratory records) for each patient. The monitoring visits provide the PI with the opportunity to evaluate the progress of the study, to verify appropriate consent form procedures, review drug accountability and to verify the accuracy and completeness of CRFs, to resolve any inconsistencies in the study records and to assure that all protocol requirements, applicable FDA regulations, other requirements, and Investigator's obligations are being fulfilled.

Furthermore, this study will fall under the purview of the Stephenson Cancer Center Data Safety Monitoring Committee (DSMC).

9.7 Data Disclosure and Patient Confidentiality

Patient medical information obtained as a result of this study is considered confidential. Disclosure to third parties other than those noted below is prohibited. All reports and communications relating to patients in this study will identify each patient only by their initials and number. Medical information resulting from a patient's participation in this study may be given to the patient's personal physician or to the appropriate medical personnel responsible for the patient's welfare. Data generated as a result of this study are to be available for inspection on request by FDA or other government regulatory agency inspectors, the clinical trial office auditors and monitors, University of Oklahoma Office of Compliance, and the Investigational Review Board (IRB).

All laboratory specimens, evaluation forms, reports, and other records that leave the site will be identified by a coded number and/or initials to maintain patient confidentiality. All study records will be kept in a locked file cabinet or other secured area. All computer entry and networking programs will be identifiable only by coded numbers and/or initials. Patient personal medical information may be reviewed by representatives of the Sponsor, of the IRB of record, University of Oklahoma Office of Compliance, or of regulatory authorities in the course of monitoring the progress of the clinical trial. Every reasonable effort will be made to maintain such information as confidential.

10 STATISTICAL CONSIDERATION

10.1 Consideration for Sample Size

The primary objective is to ensure patients can tolerate a complete induction course of combination therapy as defined by the ability to receive at least 5 of 6 treatments of BCG + avelumab within eight weeks of starting treatment. By using a modified 3+3 design for DLT observation, we expect to enroll 3~6 patients for dose level 1. If dose level 1 is not tolerated, then an additional 3~6 patients will be enrolled in dose level -1.

The most important secondary objective is to evaluate the feasibility of remaining on combination treatment to complete Month 6 maintenance therapy without dose-limiting toxicity. Therefore, an additional 12~15 patients will be enrolled and will receive the final dose. The proportion of patients completing Month 6 maintenance will be calculated and a 95% confidence interval constructed for the completion rate. The expected completion rate is about 60%. However, the final sample size was obtained from feasibility and not formal power analysis. With 18 patients at the final dose and an expected completion rate of 60%, the lower bound of the two-sided Wilson Score 95% confidence interval (CI) would be 37.6%. Although this lower limit was not clinical meaningful, it is provided to show the width of the CI given a desired 60% completion rate and the small sample size.

In order to enroll 18 evaluable patients for dose expansion cohort, we may need to screen up to 27 patients if dose level -1 will be evaluated as the final dose level since we expect a percentage of these patients to be screen failures or withdrawals.

10.2 Analytic Plan

Only evaluable patients as defined in Section 8.1.1 will be included in the statistical analysis. The proportion of patients receiving a complete induction course (at least 5 of 6 treatments of each BCG and avelumab within eight weeks of starting treatment) at 3 months and at 6 months will be calculated and a 95% Wilson score confidence interval constructed for the completion rate.

The 3-month and/or 6-month complete response (CR) rates will be summarized as the proportion (and 95% CI) of patients with complete tumor response at month 3 or 6 of study treatment.

Kaplan-Meier curves will be generated for overall survival, duration of response, progression-free survival, cystectomy-free survival, time to recurrence, and time to high-grade recurrence. Median survival time and 95% confidence intervals will be calculated. The EORTC QLQ-C30 questionnaire functional scales, symptom scales, and global health and quality of life scale will be summarized.

Frequency and severity of adverse events will be tabulated by body system, type and maximum grade. Serious adverse events will be listed.

Interim analysis

An interim safety analysis will be conducted when 3~6 patients have received ≥ 5 doses of BCG treatment in dose level 1. If the combination therapy in dose level 1 is not tolerated (2 or more patients experience a DLT), dose level -1 will be evaluated in additional 3~6 eligible patients. The decision rule is fully described in Section 5.2 Overall Study Design.

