2.1.2 Secondary Objectives

- To evaluate the feasibility and tolerability of combination therapy with BCG + avelumab as measured by the endpoint of 6 month treatment completion rate based on patients completion of at least 2 of 3 treatments within a 5 week period at the 6 Month maintenance treatment.
- To evaluate 3-month complete response (CR) rate, 6-month CR rate, recurrence free survival (RFS), cystectomy-free survival (CFS), and overall survival.

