2.2.2 Secondary Endpoints

- 6 Month maintenance treatment completion as defined as completion of at least 2 of 3 maintenance treatments within a 5-week period without unacceptable toxicities or disease progression. Disease status will be evaluated based on cystoscopy and urine cytology prior to maintenance therapy.

Patients with persistent or recurrent high-grade disease at 6 Month cystoscopy will be taken off treatment. Low-grade recurrence will be tolerated without treatment interruption.

- 3-month and 6-month complete response (CR) based on negative cystoscopy and urine cytology.
- Recurrence free survival (RFS) at 6 and 12 months, defined as proportion of patients who are alive and free of persistent or recurrent NMIBC based on cystoscopy, cytology and/or biopsy.
- Progression-free survival (PFS) at 6 and 12 months, as defined by time from day of first treatment to first progression to higher grade or stage, including muscle-invasive disease or death from any cause
- Cystectomy-free survival (CFS), defined as time from study initiation to cystectomy or death
- Overall survival, defined as time from day of first treatment to death from any cause

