6.4 Dose Modification or Discontinuation

Study treatment dosing interruptions are permitted in the case of medical / surgical events or logistical reasons not related to study therapy (eg, surgery, unrelated medical events, patient vacation, and/or holidays). Patients should be placed back on study therapy within 3 weeks of the scheduled interruption for intravesical-BCG or 12 weeks for avelumab, unless otherwise discussed with the Principal Investigator.

Toxicity and grades will be classified using the NCI Common Terminology Criteria for Adverse Events (CTCAE) version 5.0. A copy of the CTCAE version 5.0 can be downloaded from the CTEP website (https://ctep.cancer.gov/protocolDevelopment/electronic_applications/docs/CTCAE_v5_Quick_Reference_5x7.pdf). Safety plan for this study is described in [sections 6.4.1, 6.4.2](#), and [section 9](#).

Interruption of intravesical-BCG does not preclude continuation of avelumab and vice versa. For instance, if an AE is attributed to intravesical-BCG during the study treatment, then avelumab will be continued while the BCG held. While BCG is held, the patient will continue to receive avelumab, be monitored for safety, and will resume intravesical-BCG within 3 weeks if the toxicity resolves. If the AE is immune related and attributed to avelumab; then BCG will be continued while the avelumab is held.

In case treatment interruption for one of the investigational drugs (avelumab or BCG) is required for drug-related toxicity, the dose of the other drug may also be interrupted based on the guidance provided for toxicity management, product labeling, and institutional guidelines according to investigator's best medical judgement.

Note: If the patient does not receive 5 doses of scheduled 6 doses of BCG within eight weeks at the time of induction, then the patient is considered treatment failure.

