8 EVALUATION CRITERIA

8.1 Safety Evaluation

Toxicity assessment is required prior to each BCG and/or avelumab treatment. Toxicity and grades will be classified using the NCI Common Terminology Criteria for Adverse Events (CTCAE) version 5.0. Dose limiting toxicity (DLT) will be monitored during the first 6 weeks of induction treatment with intravesical BCG and IV avelumab. Definition of DLT is described in [section 5.2.1](#).

Completion rate of induction therapy with combined BCG + avelumab is defined as completion of at least 5 of 6 treatments of each BCG and avelumab within 8 weeks during BCG induction phase.

Six-month treatment completion rate will be based on patients' completion of at least 2 of 3 BCG treatments within each 5 week period at the 6 Month maintenance treatment.

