5. The following may be considered as exceptions to DLTs: 1.
- a. Grade 3 nausea, vomiting, or diarrhea and Grade 4 vomiting or diarrhea in the absence of maximal medical therapy that resolves in 72 hours.
 - b. Grade 3 fatigue lasting < 5 days.
 - c. Grade 3 hypertension that can be controlled with medical therapy.
 - d. An increase of indirect (unconjugated) bilirubin indicative of Gilbert's syndrome.
 - e. Serum lipase and/or serum amylase CTCAE Grade 3 ≤ 7 consecutive days without clinical signs or symptoms of pancreatitis.

ii. **Definition of DLT Evaluable Population**

1. Patients enrolled in safety lead-in cohort who receive at least 4 doses and complete the DLT observation period (the first 42 days of induction treatment), unless the patient discontinued the study treatment due to a DLT.

8. Antitumor Evaluation

- a. The proportion of patients receiving a complete induction course (at least 5 of 6 treatments of BCG + avelumab within eight weeks of starting treatment) at 3 months and at 6 months will be calculated and a 95% Wilson score confidence interval constructed for the completion rate.
- b. The 3-month and/or 6-month complete response (CR) rates will be summarized as the proportion (and 95% CI) of patients with complete tumor response at month 3 or 6 of study treatment. Patients who remain CR at end of study (EOS) are censored at their last cystoscopy date.
- c. The duration of response will be calculated as time from the date of first response (complete response (CR), partial response (PR), pathological complete response (pCR)) to the first date of non-response. Duration of response will be summarized using the Kaplan-Meier method. Median duration of response with 95% CI will be computed. Results will be presented in tabular and graphic form, as appropriate.
- d. Progression-Free Survival (PFS) at six month and twelve months is defined as the time in months from the first dose of the drug to the date of death or the first documented date of progression, whichever comes first. For patients who did not die and did not have progression, the PFS is censored at the last documented tumor assessment. Survival curve for PFS will be generated using the Kaplan-Meier method. Median PFS with 95% CI will be computed. Those without an event are censored at their last valid tumor assessment, or at the last tumor assessment before patient start of the new therapy if a patient has started new anti-cancer therapy.

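### Month 6 maintenance completion, the leading secondary endpoint, has three differing definitions, and the analysis sections attach its time point to induction instead

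*Protocol*

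**What the plan says.** **Objective and precision.** Protocol 2.1.2 sets the aim: "To evaluate the feasibility and tolerability of combination therapy with BCG + avelumab as measured by the endpoint of 6 month treatment completion rate". Protocol 10.1 ranks this first among the secondary objectives, describes it as staying on combination treatment without DLT, and states: "The proportion of patients completing Month 6 maintenance will be calculated and a 95% confidence interval constructed for the completion rate". It expects about 60% completion and gives a Wilson lower bound of 37.6% with 18 patients. SAP 3.b.ii repeats this.

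**Definition.** Protocol 2.2.2 asks for "completion of at least 2 of 3 maintenance treatments within a 5-week period without unacceptable toxicities or disease progression" and names no drug. Protocol 8.1 asks for "completion of at least 2 of 3 BCG treatments within each 5 week period at the 6 Month maintenance treatment". For induction, the same section asks for "completion of at least 5 of 6 treatments of each BCG and avelumab within 8 weeks during BCG induction phase". SAP 2.b.i keeps the 2.2.2 dose count but puts DLT in place of unacceptable toxicities.

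**Analysis.** Protocol 10.2 gives the induction rate, with the words "within eight weeks of starting treatment) at 3 months and at 6 months will be calculated and a 95% Wilson score confidence interval constructed". SAP 8.a has the same sentence ("at least 5 of 6 treatments of BCG + avelumab within eight weeks of starting treatment) at 3 months and at 6 months") under the heading Antitumor Evaluation. Neither names maintenance.

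**Population.** Protocol 10.2 points to the set in 8.1.1, patients with at least one dose of BCG and avelumab. SAP 5.a uses a similar set for compliance and safety. SAP 5.c assigns the antitumor measures of Section 8 to a set that generally requires at least 5 induction doses. SAP 7.a also restates induction completion, under DLT Analysis.

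**Holding one drug.** Protocol 6.4 says: "If the AE is immune related and attributed to avelumab; then BCG will be continued while the avelumab is held". Its next paragraph allows the other drug to be interrupted too. Protocol 6.4.1 allows avelumab to be interrupted for up to 12 weeks.

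**The concern.** The Month 6 rate is the reason given in Protocol 10.1 for enrolling the additional 12 to 15 patients. Its purpose is estimation, so its numerator and denominator carry all of its meaning. As written, two analysts could follow different sections and report different rates: BCG only or combination, and with or without a toxicity condition that operates at Month 6. The BCG-only count could credit a patient who received no avelumab at Month 6 as evidence that the combination is feasible. A related but separate question is which patients form the denominator of the induction rate.

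**Working it through.** **1. The plan's own figure.** Inputs from Protocol 10.1: p = 0.60, n = 18, two-sided 95%, z = 1.96. The Wilson limits are [p + z²/2n ± z√(p(1−p)/n + z²/4n²)] / (1 + z²/n).

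- z²/2n = 3.8416/36 = 0.1067, and 1 + z²/n = 1.2134.
- Root term: 1.96 × √(0.24/18 + 3.8416/1296) = 1.96 × √0.016298 = 0.2502.
- Lower: (0.60 + 0.1067 − 0.2502)/1.2134 = 37.6%. Upper: (0.60 + 0.1067 + 0.2502)/1.2134 = 78.9%.

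The stated 37.6% reproduces and is not in dispute.

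**2. Timing.** Induction completion is settled at 8 weeks, day 56. One cycle is 84 days (Protocol 6.3.1), so Month 3 starts about day 85 and Month 6 about day 2 × 84 + 1 = 169. An induction rate quoted at 3 and at 6 months is the same number. The DLT period closes on day 42, which is 169 − 42 = 127 days before Month 6 begins. DLTs are monitored in the lead-in only (Protocol 5.2.1), so the 12 to 15 expansion patients, 67% to 83% of 18, are outside that monitoring altogether.

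**3. The three definitions side by side.**

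| Source | Drugs counted | Toxicity condition | Progression condition |
|---|---|---|---|
| Protocol 2.2.2 | not named | unacceptable toxicities | yes |
| Protocol 8.1 | BCG only | none | none |
| SAP 2.b.i | not named | DLT | yes |

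**4. Can BCG-only and combination completion differ?** Yes. Under 6.4 BCG may continue while avelumab is held, and the permitted hold of 12 weeks (84 days) exceeds the 5-week window (35 days). Such a patient can meet the 8.1 count with no avelumab at Month 6. One patient is 1/18 = 5.6 points. Assume 11 of 18 meet the BCG count, and that 0, 1 or 2 of them had no avelumab at Month 6:

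| Without avelumab | Combination rate | Wilson 95% |
|---|---|---|
| 0 | 11/18 = 61.1% | 38.6 to 79.7 |
| 1 | 10/18 = 55.6% | 33.7 to 75.4 |
| 2 | 9/18 = 50.0% | 29.0 to 71.0 |

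**5. Induction denominator.** Assume 18 evaluable completers, plus 0, 2 or 4 treated patients who were replaced because they had fewer than 5 doses for reasons other than related grade 3-4 events. The SAP 5.c set gives 18/18 = 100% (82.4 to 100) in each case. The at-least-one-dose set gives 18/18 = 100%, 18/20 = 90.0% (69.9 to 97.2) or 18/22 = 81.8% (61.5 to 92.7). SAP 5.c does keep patients whose missed doses were due to related grade 3-4 events. With an assumed 3 of these among 18, its rate is 15/18 = 83.3% (60.8 to 94.2).

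**The case against.** The strongest reply is that these are drafting slips and that the intention can be recovered. Much of that stands.

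- **A reader might infer that the Month 6 analysis is missing.** It is not: Protocol 10.1 and SAP 3.b.ii state the proportion and its interval. The 10.2 and SAP 8.a sentence is probably a merge of two rates. It still has to be corrected, because it is the operative analysis text.
- **A reader might infer that Month 6 toxicity goes uncounted.** It does not in general. Toxicity that prevents 2 of 3 treatments in 5 weeks fails the dose count. The empty DLT condition matters only for patients who have toxicity and still receive 2 of 3.
- **A reader might infer that the protocol has no criteria for unacceptable toxicity.** Protocol 9.1 places the toxicity stopping rules in Tables 2-4 and 6, and 6.4.2.1 and 6.7 add discontinuation rules. What is missing is a link from the endpoint in 2.2.2 to those rules.
- **A reader might infer that SAP 5.c forces the induction rate to 100%.** It does not, because it keeps patients with related grade 3-4 events. One can also argue that induction completion is not an antitumor measure, so that 5.c never applies to it. SAP 5.a, SAP 7.a and Protocol 10.2 support that reading, but the placement of 8.a in Section 8 leaves the matter open.
- **The BCG-only count appears in Protocol 8.1 alone.** That is correct, and an analyst working only from the SAP would not meet it. But 8.1 is the protocol's evaluation section, and it names each drug for induction, so its BCG-only wording for Month 6 reads as a rule.

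**Conclusion.** The concern holds as an inconsistency in specification and should be fixed before analysis. Three conflicts are plain in the text: the six-month time point attached to a week-8 endpoint, the BCG-only count against a combination objective, and a DLT condition that does nothing at Month 6. The population question is secondary. Applying SAP 5.c would drop some treated non-completers and so bias the induction rate upward.

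The size is 5.6 points per reclassified patient at n = 18. All the shifted counts above are assumptions, since the documents give no expected number of patients without avelumab at Month 6 or of replaced patients, and the intervals overlap widely. No decision threshold depends on the Month 6 rate, so no go or stop decision is affected. What suffers is the meaning of the reported rate.

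**What to change.** 1. In Protocol 10.2 and SAP 8.a, remove the 3- and 6-month time points from the induction sentence. Add a separate sentence for the proportion completing Month 6 maintenance, with a Wilson 95% interval.
2. Reconcile Protocol 2.2.2, Protocol 8.1 and SAP 2.b.i into one Month 6 definition that matches the combination objective. One candidate is at least 2 of 3 doses of each drug within 5 weeks, without unacceptable toxicity or disease progression, with BCG-only completion as a supporting line. The sponsor must confirm the rule, because 2.2.2 names no drug.
3. Replace the DLT wording in SAP 2.b.i, Protocol 10.1 and SAP 3.b.ii with that of 2.2.2. Link unacceptable toxicities to toxicity recorded as the reason for discontinuing either drug under the existing rules (Tables 2-4 and 6, 6.4.2.1, 6.7). Section 6.7 alone is not enough: it covers stopping both drugs and may miss a patient who stops avelumab only. No new clinical rule is needed.
4. State in the SAP that both completion rates use the at-least-one-dose population (SAP 5.a, Protocol 8.1.1) at the final dose. Move 8.a out of Antitumor Evaluation and place it beside 7.a.
5. Editorial: Protocol 6.3.2 calls Month 6 completion the primary outcome, against 2.1.1 and 2.2.1. Reconcile them.

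**Cost.** A protocol amendment with written IRB approval (Protocol 13.5) and a SAP revision. The combination rate can only equal or fall below the BCG-only rate, and the induction rate can only stay or fall when the added patients did not complete. Data capture needs a check. Section 6.4.2.1 puts BCG dose and schedule changes on the CRFs, but 6.7 puts the discontinuation reason in the medical records. Confirm that the CRFs hold the Month 6 avelumab doses and the reason for discontinuing either drug.
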